7.0 Expected Risks/Benefits

Risk associated with the medical history assessment

Discomfort could be felt by participants when answering questions about their medical history.

Risk associated with the physical function battery

There is a slight risk of falling during the balance testing.

Risk associated with the 6 minute walk

There is a slight risk of abnormally high blood pressure, shortness of breath, muscle injury, and muscle soreness. The risk of serious adverse events with maximal exercise testing has been estimated to be 0.5 per 10,000 tests (Stuart, 1980 Chest), the risk of death associated with a 6-minute walk is currently not known, but is considered minimal risk. The exercise test (6 minute walk) proposed in this study is considered no more than usual activity of daily living and is considered moderate intensity exercise. There is a risk that underlying disease may be uncovered during study participation. This would most likely be undiagnosed cerebrovascular disease, previous stroke or mini-stroke. These findings would be immediately related to the patient and the providers (upon patient approval). These findings may require additional testing and procedures as deemed necessary by the patient's provider.

Risks associated with the walking exercise training

There is a slight risk of injury associated with exercise training in a sedentary population. There is a slight risk of abnormally high blood pressure, shortness of breath, muscle injury, and muscle soreness associated with exercise training in a sedentary (not used to exercise) population. The risk of serious adverse events with maximal exercise testing has been estimated to be 0.5 per 10,000 tests (Stuart, 1980 Chest), the risk of death associated with walking exercise training is currently not known, but is considered minimal risk. The exercise training proposed in this study is considered no more than usual activity of daily living and is considered moderate intensity exercise. There is a risk that underlying disease may be uncovered during study participation. This would most likely be undiagnosed cerebrovascular disease, previous stroke or mini-stroke. These findings would be immediately related to the patient and the providers (upon patient approval). These findings may require additional testing and procedures as deemed necessary by the patient's provider.

Risks associated with the venipuncture (blood draw)

The blood draw may cause pain and bruising. There is a slight risk for infection, lightheadedness and fainting.

Risk associated with the cognitive function questionnaires.

There is a slight risk that participants will feel uncomfortable with filling out the questionnaires. Participants could find answering the questions boring and/or tiring. We will monitor the progress and allow participants to take breaks as needed. If they become upset or uncomfortable, they may skip a given question.

Risks associated with the MRI:

The MRI does not use x-ray radiation or radioactive material. The magnetism of the machine attracts certain metals, which could put participants at risk. Therefore, people with pacemakers, infusion pumps, metal prostheses, metallic-backed transdermal patches or metallic shrapnel will be excluded from the study. A checklist will be completed that addresses issues of MRI safety. Some people may feel somewhat closed-in (claustrophobic) during the MRI procedure. The MRI scans can get quite noisy and this may cause some discomfort. We will provide padding, a blanket, and ear plugs to ensure comfort. This risk is minimized by careful screening by qualified research personnel prior to entry into the MRI room. Subjects with metal implantations will not be recruited. Participants' can withdraw at any time and we will closely monitor them to ensure safety and comfort.

Risks associated with ultrasound procedure:

There could be pressure felt on the neck from the hand-held tonometer, which might make participants feel uncomfortable. The inflation of the blood pressure cuffs might feel too tight and cause discomfort (similar to that of having a blood pressure measured in clinic).

The blood pressure cuff could feel too tight and it may cause discomfort and pain.

There might be pressure on the neck from the ultrasound Doppler transducer, which could feel uncomfortable

If any of these occur the measurement will stop immediately.

8.0 Data Collection and Management Procedures

Results from all measurements, and questionnaires will be recorded on coded source documents before being entered into the electronic database that is password protected and housed on a secure CON server that only the PIs and statistician have access to. Source documents will be stored in a locked file cabinet in a locked office that only the PIs have access to. coded exercise data from the heart rate monitor and actigraph will be downloaded at each follow-up

visit to a password protected secure CON server and analyzed before being entered into the main database as described above.

9.0 Data Analysis

[name] of the College of Nursing statistician will conduct all analyses. The apriori stated analysis is listed below.

This is a pilot study for feasibility. For these pilot data we will emphasize descriptive statistics such as means, standard deviations, effect sizes, medians, interquartile ranges, frequencies, and percentages to demonstrate the feasibility of recruitment, adherence, and retention, treatment effects over time, and proof of concept. Our statistical approach for a full trial of these hypotheses will be Generalized Linear Mixed Models (GLMM) with an identity link function for a continuous outcome or a logit link function for a binary outcome. Conceptually, GLMM is a more advanced version of repeated measures ANOVA that can account for potential correlation among multiple measurements over time while having flexibility in fitting outcomes with different distributions (such as normal, binomial or Poisson, etc.). One advantage of this approach over repeated measures ANOVA is that there is no assumption that participants are measured at every, or even the same, time points. Therefore, these models are very flexible at handling missing data. Participants who have a missing observation are not excluded, thus, this produces the intention to treat (ITT) full information maximum likelihood (FIML) model. Conducting these models on pilot data help with sample size calculations for a future R01 submission.

10.0 Quality Control and Quality Assurance

Data will be evaluated for protocol adherence during weekly meetings with the PIs and the study manager. [name] will evaluate all data for quality during weekly study meetings. Biweekly visits will be conducted by the PI to ensure that data collection is carried out according to the protocol.

11.0 Data and Safety Monitoring

Serious adverse events will be monitored and tracked at each follow-up period and biweekly phone calls. Patients will be queried at the biweekly phone calls and at 24 weeks if they have had any visits to the emergency department or hospitalizations (see attached checklist). We will also ask if they have had any symptoms of cardiac-related problems such as chest, arm or jaw pain while exercising or not exercising. Data will be recorded on an excel spreadsheet and reviewed by the PI at weekly study meetings. Any unanticipated adverse events or problems will be reported to the IRB within 7 days on notification. [name], ATC, FSVM, FAHA will monitor safety data. Subjects are free to withdraw from the study at any time. If a subject withdraws from the study we will ask the subject (only once) if they are willing to come back for the follow-up tests. If the subject does not want to complete the study, no further contact attempts will be conducted and the subject will be discontinued from the study (this will be reported at the annual continuing review).

This study is funded by the Midwest Roybal Center for Health Promotion and Translation and is required to follow their NIH approved DSMB plan outlined below: The PI will be responsible for ensuring participants' safety on a daily basis. The Safety Officer (SO; [name], Roybal PI) in conjunction with a Data Safety Monitoring Roybal Center Committee will act in an advisory capacity to the NIA Director to monitor participant safety, evaluate the progress of the study, to review procedures for monitoring the confidentiality of the data, the quality of data collection, management, and analyses.

Safety Officer Membership and Affiliation.

[name], Midwest Roybal grant PI, has accepted the position as the Safety Officer and will work with the study PI to review pilot study data and safety monitoring.

Title: Co-Director, Center for Research on Health and Aging and Professor, Community Health Sciences

Organization/Affiliation: Institute for Health Research and Policy and School of Public Health, UIC

Data Safety Monitor Committee

[name] will serve as chair of the committee, and as SO for any adverse event reports. Other members will include [name] (Kinesiology), [name] (Medicine), and [name] (School of Public Health)

Conflict of Interest for SO.

The SO and DSM committee will adhere to the Conflict of Interest Policy and procedures of the University of Illinois.

The PI will meet semiannually with the DSM Committee, either in-person or by teleconference call to review study progress, data quality, and participants' safety. Written summary reports will be submitted twice a year and will include a detailed analysis of study progress, data and safety issues. The PI will be informed of serious adverse events as soon as they occur and will notify the SO within 24 hours of notification. In addition, serious adverse events will be reported to the UIC IRB and NIA consistent with their established protocols.

Content of Data and Safety Monitoring Report/SO Reports.

The content of the SO report will include study status/quality, participant descriptive information, adverse events, and dropout rates/reasons.

Protection of Confidentiality.

Data will be presented to the SO and DSM committee in a blinded manner during meetings and in written reports. The content of the SO reports and discussions will be treated as confidential. Participant identities will not be known to the SO.

SO and DSM committee Responsibilities.

The responsibilities of the SO DSM committee include:

- Review the research protocol, informed consent documents and plans for data safety and monitoring;
- Recommend subject recruitment be initiated after receipt of a satisfactory protocol;
- Evaluate the progress of the trial, including periodic assessments of data quality and timeliness, recruitment, accrual and retention, participant risk versus benefit, performance of the trial sites, and other factors that can affect study outcome;
- Consider factors external to the study when relevant information becomes available, such as scientific or therapeutic developments that may have an impact on the safety of the participants or the ethics of the trial;
- Review study performance, make recommendations and assist in the resolution of problems reported by the Principal Investigator;
- Protect the safety of the study participants;
- Report to NIA on the safety and progress of the trial;
- Make recommendations to the NIA and the Principal Investigator concerning continuation, termination or other modifications of the trial based on the observed beneficial or adverse effects of the treatment under study;
- Ensure the confidentiality of the study data and the results of monitoring; and
- Assist the NIA by commenting on any problems with study conduct, enrollment, sample size, and/or data collection.

Serious adverse events will be monitored and tracked during each phone call (every two weeks). Patients will be queried they have had any visits to the emergency department or hospitalizations. We will also ask if they have had any symptoms of cardiac-related problems such as chest, arm or jaw pain while exercising or not exercising. Lastly, we will ask patients if they have had any falls. Data will be recorded on an excel spreadsheet and reviewed by the PI and study team at weekly study meetings.

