3.0 Objectives/Aims

This is a pilot study for feasibility. The objective of this study is to test the hypothesis that older participants with moderate/severe chronic kidney disease (CKD) and preclinical cognitive impairment randomized to a 6-month home-based exercise program (n=12), will improve cognitive functioning and white matter integrity (WMI), compared to participants in a usual care control group (n=12). Our central working hypothesis is that the accelerated cognitive decline that occurs in CKD results, in part, from a vascular-dysfunction induced impairment of white matter integrity that is superimposed on a neurodegenerative process, and that exercise training may provide a cerebro-protective effect by improving systemic and cerebral vascular health.

Aim 1: Determine the feasibility and preliminary efficacy of a 6-month home-based exercise program to improve or maintain cognitive function in older participants with moderate/severe CKD and preclinical cognitive impairment, compared to usual care control group.

Hypotheses: Participants in the exercise group compared to the usual care control group at 6-months will:

- H1a. Demonstrate a higher score on composite global cognitive functioning.
- H1b. Demonstrate higher scores on executive functioning, learning/memory, and attention/information processing.

Aim 2. Determine the cerebro-protective effect of a 6-month exercise program compared to usual care on white matter integrity as quantified by Diffusion Tensor Imaging (DTI)-derived MRI measures of mean diffusivity (MD) and fractional anisotropy (FA). Intact white matter is important because it allows the brain to function properly and these are indices of white matter integrity.

- H2a. Participants in the exercise group will demonstrate an improvement in overall white matter integrity as measured by DTI, i.e., lower MD and higher FA, compared to control.

- H2b. Change in cognitive function will be positively correlated with change in WMI.

Aim 3 (secondary MRI outcomes): Determine the cerebro-protective effect of a 6-month exercise program compared to control on hippocampal volume and cerebral blood flow.

Hypothesis: Participants in the exercise group will have a larger hippocampal volume and improved cerebral blood flow post 6-month intervention, compared to the control group.

Study Duration: 12 months. Study duration for enrolled participants is anticipated to be 27 weeks.

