3. c. Following these procedures participants will be asked to complete several questionnaires to assess their cognitive function. These questionnaires will be performed pre- and post-intervention with alternative forms where available to avoid practice effects. In addition to an overall global composite of cognitive functioning, we will evaluate the following domains of functioning with the below noted tests. (time~1 hour): The forms are titled: Learning & Memory=California Verbal Learning Test-II (CVLT-II); Attention/Information Processing=Trail Making Test Part A (TMT-A) and Digit Symbol Substitution Test (DSST); Executive Functioning, Phonemic and Semantic Fluency=Trail Making Test Part B and part M (TMT-B) and Digit Span subtest (DSp); Global Cognition=MOCA and WTAR (please see enclosed questionnaires). Quality of life will be assessed via the kidney disease quality of life questionnaire. These questionnaires will be administered at baseline and at 24 week follow up. The study satisfaction questionnaire will be administered at 24 weeks only.

Cognitive Outcomes (Table 1) will be performed pre- and post-intervention with alternative forms where available to avoid practice effects. In addition to an overall global composite of cognitive functioning, we will evaluate the following domains of functioning with the below noted tests. (time~1 hour)

Table 1. Cognitive Protocol

Domain	Tests	Outcome variables
Learning & Memory	California Verbal Learning Test-II (CVLT-II)	CVLT-II: Trials1-5 and learning slope; Long Delay Free Recall and Recognition Memory Discriminability
Attention/Information Processing	Trail Making Test Part A (TMT-A); Digit Symbol Substitution Test (DSST)	TMT-A time to completion and errors; DSST time to completion and errors
Executive Functioning	Phonemic and Semantic Fluency; Trail Making Test	Total correct words produced for Phonemic and Semantic fluency

	Part B (TMT-B); Digit Span subtest (DSp)	separately; TMT-B time to completion and errors; DSp total score
Global Cognition	MOCA and WTAR*	Total MOCA score; WTAR Estimated verbal IQ

*WTAR will only be given once as premorbid IQ is not anticipated to change with intervention

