The monthly meetings (once per month) will occur at months, 1, 2, 3, 4, and 5 following randomization. The PI and study staff will continue to work with the participants to assess their readiness to do exercise; 2) address perceived barriers to exercise, and 3) provide support and address concerns related to the exercise program. The meetings will last 30 minutes. We will assess for any adverse events during the bi-weekly phone calls using the document title "Adverse Event Monitoring". The total number of visits in the exercise group is 11.

Usual medical care control group

The usual care group will receive standard instructions on exercise for patients with kidney disease. These documents are titled "Exercise Recommendations" and "work effort scale". This is similar to what is commonly done in clinical practice. The control group will not receive an exercise prescription or heart rate monitor. Participants will be contacted via phone biweekly to answer any questions and ensure continued study participation. In order to minimize any feeling of disenfranchisement in the control group we will offer them the exercise training prescription following all post-test data collection procedures. The usual care group will NOT meet monthly. We will assess for any adverse events during the bi-weekly phone calls using the document title "Adverse Event Monitoring". The total number of visits for the usual care group is 5.

Ten participants with an eGFR of >60 ml/min will only undergo baseline testing and not partake in the intervention or follow up. We will ask if the participants with an eGFR >60 ml/min prefer to only to the baseline versus intervention.

Follow-up testing will occur at 24 weeks over 2 visits about 1 week apart. During the follow up testing we will ask participants to perform one 6-minute walk test and the short physical performance battery, and the NIH toolbox measures as described above, as well as completing the questionnaires and imaging procedures described above.

During the 24-week visit we will query patients using structured interviews and open-ended questions as to whether participants liked the independent home-based walking program. Study satisfaction will be assessed using a likert scale and open-ended question at the end of the 24 week follow up test..

Physical activity and exercise monitoring and Assessment of Adherence to Exercise Rehabilitation Program (fidelity of treatment):

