12.0 Statistical Considerations

[name] of the College of Nursing statistician will conduct all analyses. The apriori stated analysis is listed below.

This is a pilot study for feasibility. For these pilot data we will emphasize descriptive statistics such as means, standard deviations, effect sizes, medians, interquartile ranges, frequencies, and percentages to demonstrate the feasibility of recruitment, adherence, and retention, treatment effects over time, and proof

of concept. Our statistical approach for a full trial of these hypotheses will be Generalized Linear Mixed Models (GLMM) with an identity link function for a continuous outcome or a logit link function for a binary outcome. Conceptually, GLMM is a more advanced version of repeated measures ANOVA that can account for potential correlation among multiple measurements over time while having flexibility in fitting outcomes with different distributions (such as normal, binomial or Poisson, etc.). One advantage of this approach over repeated measures ANOVA is that there is no assumption that participants are measured at every, or even the same, time points. Therefore, these models are very flexible at handling missing data. Participants who have a missing observation are not excluded, thus, this produces the intention to treat (ITT) full information maximum likelihood (FIML) model. Conducting these models on pilot data help with sample size calculations for a future R01 submission.

This is a pilot study investigating the feasibility and proof-of-concept. There is no power-calculation for this study: This study may not be powered to find statistically significant differences between groups due to the smaller sample size. Based on previous studies, we do expect to find at a minimum a trend for improvement cognitive function and brain structure. We expect to be able to use these data for determination of the necessary sample size for detection of significant differences between groups

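### A withdrawing participant is asked once to return for the 24-week tests, with no smaller option written and no adverse event query, so each decliner's only post-randomization cognitive score is lost

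*Combined protocol and SAP*

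**What the plan says.** Section 11.0 (Data and Safety Monitoring) sets the rule for a participant who withdraws from the study: "we will ask the subject (only once) if they are willing to come back for the follow-up tests". If that person does not want to complete the study, "no further contact attempts will be conducted and the subject will be discontinued from the study".

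Section 6.0 (Study Design and Procedures) states what those tests are: "Follow-up testing will occur at 24 weeks over 2 visits about 1 week apart". They comprise the 6-minute walk, the short physical performance battery, the NIH Toolbox, the questionnaires and the imaging. Of the cognitive battery in Table 1, section 6.0 says: "These questionnaires will be administered at baseline and at 24 week follow up".

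Adverse events are asked about at the biweekly calls (sections 6.0 and 11.0), and emergency visits and hospitalizations also at 24 weeks (section 11.0). The investigator notifies the safety officer of a serious event within 24 hours of learning of it. On periodic reporting, section 11.0 says: "The content of the SO report will include study status/quality, participant descriptive information, adverse events, and dropout rates/reasons".

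On missing data, sections 9.0 and 12.0 describe a mixed model and say: "Participants who have a missing observation are not excluded". Retention is named as something the pilot is to demonstrate, but no expected rate is given. The 80-87% in section 6.0 refers to adherence and compliance in earlier work.

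**The concern.** The one permitted request is for the most demanding package in the study. Some people who refuse two visits with a walk test and MRI might accept an hour of cognitive testing, or a safety call. The written rule gives staff nothing smaller to offer and then closes contact with those who decline.

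Two things are at stake. The first is Aim 1: hypotheses H1a and H1b compare cognition between arms at 6 months, and that is the only cognitive value after randomization. The effect sizes are meant to inform the sample size of a later trial, so selective loss here would carry forward. The second is safety: the plan finds adverse events by talking to participants, and those conversations stop at refusal.

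**Working it through.** **1. What a refusal removes.** Section 11.0 ends contact with a decliner. Section 6.0 places cognition at baseline and 24 weeks only, with nothing between. A decliner therefore has a baseline score and no cognitive score after randomization. Accelerometer and heart-rate data collected before withdrawal are kept, but they are not cognitive outcomes.

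**2. Whether the mixed model recovers it.** Keeping a participant in the model is not the same as observing the outcome. With two time points and the second missing, the person supplies baseline information only. The estimate then relies on decliners being like completers with the same baseline and arm (missing at random). The data cannot test this, and it is doubtful if people leave because of the exercise itself.

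**3. Safety.** Section 11.0 places no adverse event query at the withdrawal contact and gives no rule for following an open event to its outcome. Events already reported stay recorded, and dropout reasons go into the safety officer's report. What may be lost is an event since the last call that nobody asks about, and the final outcome of an event still open at refusal.

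**4. Precision (illustrative).** The plan states no power, SD or dropout figure, so there is no planned figure to reproduce. Inputs: 12 per arm (section 3.0); loss d of 10%, 20% or 30% in each arm (assumed).

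The standard error of the difference in means is SD × √(2/m), with m = 12(1 − d). Its rise is √(12/m) − 1:

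- d = 10%: m = 10.8, √(12/10.8) − 1 = 5.4%
- d = 20%: m = 9.6, √(12/9.6) − 1 = 11.8%
- d = 30%: m = 8.4, √(12/8.4) − 1 = 19.5%

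The rise equals 1/√(1 − d) − 1, so it does not depend on the starting size. That matters because section 1.0 gives 72 randomized and section 3.0 gives 12 + 12, figures that need reconciling separately.

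The 95% half-width in SD units is t(0.975, 2m − 2) × √(2/m), with m rounded to whole people:

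| Start per arm | No loss | 10% | 20% | 30% |
|---|---|---|---|---|
| 12 (m = 12, 11, 10, 8) | 0.85 | 0.89 | 0.94 | 1.07 |
| 36 (m = 36, 32, 29, 25) | 0.47 | 0.50 | 0.53 | 0.57 |

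**5. Bias (illustrative).** Let q be the fraction lost in an arm, and g the completer mean minus the mean that decliners would have had, in SD units. The completers' mean in that arm is off by q × g, so the between-arm difference is off by (q × g in exercise) − (q × g in control).

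- 20% lost in one arm only, g = 0.5 to 1.0 (assumed): 0.20 × 0.5 = 0.10 to 0.20 × 1.0 = 0.20 SD.
- 20% lost in both arms, g = 0.5 in both: 0.10 − 0.10 = 0.

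Unequal loss is plausible, because section 6.0 asks 11 visits of the exercise arm and 5 of usual care, but the documents do not predict it.

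**6. What a smaller request would recover.** The documents give nothing from which to compute this.

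**The case against.** Asking only once protects the right to leave without penalty, which matters in older adults with cognitive complaints. The study is a descriptive, unpowered pilot in which retention is itself an outcome, so refusals are informative. Both points stand. They argue against repeated approaches, not against a better-designed single one.

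A reader might infer several stronger things that the documents do not support:

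- *That the request is all-or-nothing.* Section 11.0 says only that the person is asked about the follow-up tests; it does not forbid partial attendance. MRI is conditional on being able to have it (section 6.0), and questions may be skipped (section 7.0). The gap is that no reduced option is written, so what is offered may vary between staff or arms.
- *That everyone who withdraws is never contacted again.* The no-contact rule covers only those who decline. It is also triggered by withdrawal from the study, not by stopping the walking.
- *That the question is put months before week 24.* The rule limits the number of requests, not their date.
- *That harms causing withdrawal go uncounted.* An injury that made someone leave would usually be known, dropout reasons are reported, and the exercise arm also has monthly meetings. The supportable claim is limited to the missing query at withdrawal and the outcome of events still open.
- *That the Aim 1 contrast is biased by a set amount.* A shift in one arm's mean is not a shift in the contrast, and similar loss in both arms largely cancels.

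The consent document and the Adverse Event Monitoring form are not reproduced in the protocol and may already contain terms on contact after withdrawal.

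**Conclusion.** The point holds as a cheap improvement to a stated rule. Followed as written, section 11.0 loses the only post-randomization cognitive value of each person who declines. The mixed model replaces it with an untestable assumption. The safety gap is narrower: no query at withdrawal and no provision for the outcome of an event still open.

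The size is illustrative only. A rise of about 5% to 20% in the standard error rests on an assumed 10% to 30% loss in each arm. A shift of 0.10 to 0.20 SD in the contrast needs 20% loss confined to one arm and an assumed 0.5 to 1.0 SD difference between decliners and completers; it is zero when loss and difference are equal in both arms. No figure can be put on the gain from a smaller request. None of this undermines the trial as a feasibility study.

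**What to change.** In section 11.0, keep the single contact and write down what it contains:

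- (a) Complete the adverse event form at that contact.
- (b) Offer, in order, the full 24-week follow-up tests or, failing that, one visit with the Table 1 cognitive tests only (about 1 hour by section 6.0).
- (c) Ask permission for one later phone contact about adverse events only. This call yields no Table 1 score and should not be counted as cognitive follow-up.

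Honour any refusal, use the same script in both arms, and analyse whatever is obtained under the assigned arm. Report how many people took each option, which also adds to the retention findings.

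The cost is protocol and consent wording, a short script and at most one permitted extra call per person. Some participants will have cognition without MRI. If medical records are to be used to follow open events, the consent and HIPAA authorization must cover it, because the waiver in section 13.1 is for recruitment only.
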